## 7. RADIOTHERAPY PORTS

Scrotal radiation therapy will be given to all patients.

### Timing

Radiation therapy will begin three weeks after the completion of chemotherapy, provided that WBC is  $>3000/\mu\text{l}$  and platelets  $>100,000/\mu\text{l}$ .

### Portal and treatment definition

PROPHYLACTIC SCROTAL RT

The clinical target volume (CTV) includes the contralateral testis.

### Localization and simulation

Patients must be simulated in the treatment position on a dedicated treatment simulator or CT simulator.

### Treatment technique

Patients should be treated in supine position.

Scrotal radiotherapy - CTV should be defined clinically by palpation. The contralateral testis should be treated with the direct anterior beam with electron beam 9 to 12 MeV or 6MV field bolus should be placed for patients who are treated with 6MV linear accelerator. Care should be taken to avoid unnecessary radiation to the perineum or the legs.

### Dose definition and schedule

For prophylactic scrotal RT, the following dose fractionations schedules are acceptable:

- 25 Gy in 10-15 fractions
- 30 Gy in 10-20 daily fractions

## 8. CONCOMITANT THERAPY

During treatment are recommended as concomitant therapy:

- Pre-phase therapy is recommended in older patients ( $>65$  years) with PDN 100 mg/die for 10 days and VCR 1.5 mg total dose
- G-CSF or Peg-Filgrastim as primary prophylaxis for the prevention of febrile neutropenia in older ( $>65$  years) patients in according to 2006 Update of Recommendations for the use of white blood cell growth factors (Smith TJ, Khatcheressian J, Lyman GH, et al. 2006 Update of Recommendation for use of white blood cell growth factors: an evidenced-based clinical practice guideline. J Clin Oncol 2006; 24: 3187-3205)
- Cotrimoxazole BACTRIM 3 tablets/week (or 1 x 2/day for two days/week) or Pentamidine aerosol every 15 days in patients with Bactrim allergy or in patients with G6PD deficiency throughout the treatment and consolidation phase
- In patients with Ab antiHBcAg +, Ab antiHBsAg +/- prophylaxis against hepatitis B reactivation with Lamivudine 100 mg/die from the start of the treatment to one year after the end of the treatment

All concomitant medications for medical conditions other than B-NHL are permitted, as clinically indicated.

All supportive therapies other than anti-cancer treatment needed for the management of patients enrolled in this study are permitted.

## 8.1. Permitted therapy

The following medications and support therapies that may be used if needed during this study:

- Antiviral prophylaxis with acyclovir 800-1200 mg at day since the beginning of therapy is strongly recommended in patients with herpes virus infection reactivation Additional prophylaxis with levofloxacin or ciprofloxacin will be administered in case of neutropenia  $<1.0 \times 10^9/l$ .
- G-CSF or Peg-Filgastrim is allowed and will be given according to primary physician decision in presence of neutropenia  $< 1.0 \times 10^9/l$ .
- Platelets and red blood cell transfusion are allowed, if needed with filtered and irradiated products in case of Hb  $< 8 \text{ g/dL}$  or Plts  $< 10 \times 10^9/l$ .
- Erythropoietin therapy is allowed according to ASH/ASCO guidelines
- Immunoglobulin assay is advisable once a month during the therapy with immunoglobulin replacement in case of IgG level  $< 0.3-0.5 \text{ gr/dl}$  and frequent infectious events.
- Laxatives and other prebiotics and probiotics are recommended to prevent constipation and should be administered according to standard practice
- Antiemetic agents
- Premedication for rituximab infusion with paracetamol and diphenhydramine is mandatory before each infusion of rituximab, because it may reduce infusion reactions.
- Use of corticosteroids is allowed in emergency or as pre-medication for rituximab infusion

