## TREATMENT PROGRAM

WEEKS 1-15	- 6 cycles of CHOP on days 1 to 5, to be repeated q 21 days - Rituximab on day 0 or day 1 - IT chemotherapy: Depocyte®, 50 mg on day 0 of cycles 2, 3, 4, 5 of CHOP
WEEKS 18-22	- Methotrexate 1.5 g/m  q 14 days x 2
FROM WEEKS 24	- Scrotal prophylactic radiotherapy or involved field radiotherapy (but can be planned concomitantly to R-CHOP in patients with bilateral disease)

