### 6.2.1. CHOP dose modification

Patients will start R-CHOP every 21 days if neutrophils  $> 1.0 \times 10^9/L$  and platelets  $> 75 \times 10^9/L$ .

- If neutrophils are  $< 1.5 \times 10^9/L$  and/or platelets  $< 75 \times 10^9/L$ : R-CHOP must be delayed (after 7 days, on day +28)
- If Neutrophils  $\geq 1.5 \times 10^9/L$  and Platelets  $\geq 75 \times 10^9/L$  on Day +28 R-CHOP will be performed with no change in dose

In case of neutropenia Filgrastim or Peg-Filgastrim should be added in the following course of chemotherapy according to "2006 update of recommendations for the use of white blood cell growth factors: an evidence-based clinical practice guideline" (Journal Clinical Oncology 2006 24:3187-3205), and to primary physician judgment in order to avoid delay. Primary prophylaxis of neutropenia with filgastrim or peg-Figastim is allowed in patients over 65 years of age according to the same guidelines.

- Dose modification for sensory neuropathy. No modification as long as neuropathy does not affect function. Any decrease of function (grade 3/4) would lead to dose reduction of vincristine by 50%. If grade 4 toxicity persists after reduction of vincristine by 50%, vincristine may be eliminated from subsequent cycles.
- Prednisone dose may be decreased by 50% or discontinued if patients have increase in serum glucose to  $> 300 \text{ mg/dl}$ , or other psychological disturbances such as psychosis or anxiety attacks.

Just patients who have achieved PR/CR after three cycles of CHOP will continue therapy. All other patients will be removed from the study and will be considered for other possible therapies according to the local policy.

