## **ATTACHMENT 3**

### **Instructions for the preparation and handling of DEPOCYTE injections**

DepoCytē® should be stored in a refrigerator between 2° to 8°C (DO NOT FREEZE).

The principal investigator has to authorize those personnel having access to and the ability to administer the investigational medicinal product. This will be documented on a so called "authorised personnel form" provided by the monitor. Only qualified personnel who are familiar with procedures which minimize undue exposure to themselves and to the environment shall undertake, in a self-contained protective environment, the preparation, handling and safe disposal of DepoCytē®.

The vial must be at room temperature prior to performing the following procedures. Immediately prior to withdrawing a dose of DepoCytē®, the vial should be gently agitated by rolling the vial between the palms. Avoid excessive agitation (DO NOT SHAKE). No filtering, reconstitution or dilution is required prior to withdrawing drug. DepoCytē® must be used within 4 hours of withdrawal from the single-dose vial. Since DepoCytē® does not contain any preservatives, unused portions of each vial should be properly discarded. Do not mix DepoCytē® with any other medications.

Concurrent steroid administration is important for the prevention of drug-related arachnoiditis.

Therefore the patients should receive dexamethasone 4mg po (or iv) b.i.d. on the day of intrathecal injection. Steroid medication should be continued for 5 days after Depocytē® injection as standard part of the R-CHOP regimen (i.e., Prednisone 40mg/m^2 d 1-5)

## ATTACHMENT 4

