#### Caution: Do not administer rituximab as an intravenous push or bolus

Rituximab will be administered intravenously in an out- or in-patient setting. Oral premedication (1000 mg of paracetamol and 50-100 mg diphenhydramine hydrochloride) needs to be administered 30-60 minutes prior to starting each infusion of rituximab. Prednisone/prednisolone as part of the chemotherapy protocol will be administered in the prescribed dose before the infusion of rituximab, preferably as oral medication. A peripheral or central intravenous (iv) line will be established. Before starting the infusion, there should be a

ready supply of epinephrine for subcutaneous injection and diphenhydramine hydrochloride for intravenous injection, and resuscitation equipment for the emergency handling of anaphylactic reactions.

The infusion will be started at an initial rate of 50 mg/hour for the first hour. During the rituximab infusion, the patient's vital signs (blood pressure, pulse, respiration and temperature) will be monitored every 15 minutes (4x) for one hour or until stable and then hourly until the infusion is discontinued. If no toxicity is seen during the first hour, the dose rate may be escalated gradually (by increments of 50 mg/hour at 30 minute intervals) to a maximum of 300 mg/hour. If the first dose of rituximab is well-tolerated, the starting flow rate for administration of the second and subsequent infusions will be 100 mg/hour and then increased gradually (by 100 mg/hour increments at 30 minute intervals) not to exceed 400 mg/hour. Patients may experience transient fever and rigors with infusion. If any of the effects below are noted, the antibody infusion should be temporarily discontinued, the patient should be observed, and when the symptoms improve, the infusion should be continued but at half the previous rate.

Dose Rate	Fever	Rigors/chills	Mucosal congestion Edema	Drop in Systolic Blood Pressure
Decrease to 1/2 If any of these Events seen:	> 38.5°C	Mild/Moderate	Mild/Moderate	> 30 mm Hg

Following the infusion the intravenous line should be kept open for medications, as needed. If there are no complications, the intravenous line may be discontinued after one hour of observation.

Dosage: 375 mg/m^2 body surface

body surface	total dose
1.4 m 	525.0 mg
1.5 m 	562.0 mg
1.6 m 	600.0 mg
1.7 m 	637.5 mg
1.8 m 	675.0 mg
1.9 m 	712.5 mg
2.0 m 	750.0 mg

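### The corticosteroid passages do not fit together: prednisone that Attachment 3 relies on as Depocyte cover may be cut under 6.2.1 with no linked rule, and 8.1 omits the dexamethasone that Attachment 3 directs

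*Combined protocol and SAP*

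**What the plan says.** Five places in the protocol bear on corticosteroids.

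- **Attachment 3 (Depocyte preparation and handling).** It gives the purpose: "Concurrent steroid administration is important for the prevention of drug-related arachnoiditis". It then directs injection-day treatment: "Therefore the patients should receive dexamethasone 4mg po (or iv) b.i.d. on the day of intrathecal injection". For the days that follow it says "Steroid medication should be continued for 5 days after" the injection, and names the R-CHOP prednisone of days 1-5 as the source.
- **Section 6.2.1 (CHOP dose modification).** "Prednisone dose may be decreased by 50% or discontinued if patients have increase in serum glucose to" a level above 300 mg/dl. Psychological disturbances such as psychosis are a second trigger. Depocyte is not mentioned.
- **Section 6.1.1 (treatment schedule).** Depocyte is given on day 0 of cycles 2, 3, 4 and 5, four times in all, with no condition attached. Rituximab is on day 0 or day 1, and prednisone is on days 1-5. Dexamethasone is not listed here or in Attachment 9.
- **Sections 8, 8.1 and 8.2.** The corticosteroid line in 8.1 reads "Use of corticosteroids is allowed in emergency or as pre-medication for rituximab infusion". Section 8 says more broadly "All supportive therapies other than anti-cancer treatment needed for the management of patients enrolled in this study are permitted", and it recommends a prednisone pre-phase in patients over 65. Section 8.2 prohibits only other antineoplastic agents and experimental agents.
- **Attachment 4 (rituximab).** "Prednisone/prednisolone as part of the chemotherapy protocol will be administered in the prescribed dose before the infusion of rituximab".

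**The concern.** The primary objective (2.1) is the safety and feasibility of the combination that includes intrathecal liposomal cytarabine. Section 1.1.2 lists arachnoiditis among the serious events seen with that drug. A protection that the protocol itself calls important should therefore be set out once, and every rule that can alter it should say so.

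Here one steroid has two jobs. The prednisone is part of CHOP and also the cover after each injection, but the rule for cutting it treats it only as part of CHOP. The triggers add to the difficulty: psychosis and hyperglycaemia both appear in the 1.1.2 list of serious events seen with Depocyte, and 6.2.1 makes psychosis or high glucose a reason to cut prednisone. An event that might be related to Depocyte could thus lead to less steroid cover for the next injection.

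Two things are at stake. Patients could receive injections with less cover than Attachment 3 intends. And if the steroid given at each injection is not recorded, a neurological event in a 35-patient safety study is hard to interpret.

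**Working it through.** There is no planned figure to reproduce; the check is a comparison of texts.

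**Step 1: prednisone as Depocyte cover.** The injection is on day 0, and the five days after it are days 1-5, exactly the prednisone days in 6.1.1. Attachment 3 supplies no other steroid for those days. If 6.2.1 is applied in any of cycles 2-5, the cover on days 1-5 is halved or removed. Section 6.2 has subsections for CHOP and rituximab only. Neither it nor Attachment 3 says what then happens to the intrathecal dose or its cover. The injection-day dexamethasone is separate, and 6.2.1 does not touch it. Followed as written, the result is partial cover.

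**Step 2: the 8.1 list.** Injection-day dexamethasone is neither emergency use nor rituximab premedication, so 8.1 does not name it. But the general permission in Section 8 is wide enough to include it, the Section 8 pre-phase is another steroid use that 8.1 does not name, and 8.2 does not prohibit steroids. Section 6.1 and Section 12.4.1 both send sites to Attachment 3. So 8.1 omits the use; it does not forbid it.

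**Step 3: prednisone before rituximab.** The synopsis says "Rituximab on day 0 or day 1", and 6.1.1 agrees. With rituximab on day 0 and prednisone from day 1, protocol prednisone cannot come first. With rituximab on day 1 it can. Section 1.1.3 places infusion reactions in most patients at the first infusion, and cycle 1 has no intrathecal injection and hence no injection-day dexamethasone. The number of day-0 infusions is not given.

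**Step 4: size.** Injections that rely on the cover: 35 patients x 4 = 140 at most. How many would have reduced cover depends on a rate that the documents do not give. If 5-10% of patients had prednisone cut (assumption), that is 0.05 x 35 = 1.75 to 0.10 x 35 = 3.5 patients.

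An illustration, on assumed values only, shows why no effect is claimed. Let f be the share of patients who stop prednisone, a the arachnoiditis risk with full cover and b the risk without it. The overall risk is (1 - f)a + fb.

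| a, b (assumed) | f = 5% | f = 20% | Expected patients of 35 (full cover, then f = 5% to 20%) |
|---|---|---|---|
| 5%, 20% | 0.95 x 5% + 0.05 x 20% = 5.75% | 0.80 x 5% + 0.20 x 20% = 8.0% | 1.75, then 2.0 to 2.8 |
| 10%, 40% | 0.95 x 10% + 0.05 x 40% = 11.5% | 0.80 x 10% + 0.20 x 40% = 16.0% | 3.5, then 4.0 to 5.6 |

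The exact 95% interval is 0.7% to 19.2% for 2 events in 35, and 3.2% to 26.7% for 4 in 35. The shifts lie well inside those intervals. The illustration also treats affected patients as having no cover, which overstates the case because dexamethasone remains.

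**The case against.** The strongest reply is that a site reading the whole protocol would not go wrong. It is directed to Attachment 3 for giving Depocyte, nothing forbids the dexamethasone, and its absence from 6.1.1 and Attachment 9 matches how the protocol handles other supportive drugs: the mandatory rituximab premedication and the calcium folinate given with methotrexate are not in those places either. The prednisone rule is discretionary, a halved dose still leaves some steroid, and 10.2 lets the investigator stop treatment for safety. Steroid premedication on a rituximab day 0 is expressly allowed, and paracetamol and diphenhydramine are mandatory. Section 9.4 names only grade 3-4 haematological toxicity under safety and feasibility, so arachnoiditis is not a named endpoint.

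Most of this stands, and it settles the 8.1 point as an inconsistent list. It also softens the day-0 rituximab mismatch without removing it, since permitted premedication is not the protocol prednisone that Attachment 4 names.

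It does not answer the prednisone point. General investigator discretion is not a rule linking a prednisone cut to the intrathecal dose, and an investigator working from 6.2.1 has nothing there to show that the prednisone serves a second purpose. Nor does the wording of 9.4 put neurological events outside the safety result, because 11.2.1 requires all adverse events to be recorded whatever their severity.

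**Conclusion.** The passages are inconsistent and must be reconciled. The gap between 6.2.1 and Attachment 3 is the main point; the omission in 8.1 and the day-0 rituximab mismatch are lesser ones. Severity is moderate: no sample size, endpoint definition or analysis changes.

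Three stronger readings are tempting, and the documents do not support them.

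- A reader might infer that 8.1 forbids steroids with Depocyte. It does not, given Section 8 and 8.2.
- A reader might infer that Depocyte continues unprotected once prednisone is stopped. The protocol is silent on whether it continues: the inference rests on the unconditional schedule in 6.1.1, and 10.2 leaves room to stop. Injection-day dexamethasone would remain in any case.
- A reader might take the 140 injections as doses put at risk. They are the maximum number that rely on the cover, and the share with reduced cover is unknown.

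Nor can it be said that the measured toxicity will be biased by any stated amount, because the documents give neither a rate of prednisone reduction nor a rate of arachnoiditis. The conclusion rests on the wording alone and takes no view on which steroid rule is clinically right.

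**What to change.** Reconcile 6.1.1 (R-CHOP and intrathecal parts), 6.2.1, 8.1, Attachment 3, Attachment 4 and Attachment 9 so that they state one consistent rule. The reconciled text should say:

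1. how a reduction or stop of prednisone bears on the intrathecal dose and on its steroid cover;
2. whether and where the injection-day dexamethasone belongs in the schedule and in the list of permitted therapy;
3. how the instruction on prednisone before rituximab applies when rituximab is given on day 0.

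The sponsor's clinicians choose the rule; this review proposes none.

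On the data side, record on the CRF the steroid actually given at each intrathecal dose and over the following five days. List neurological adverse events with that information beside them. Keep this descriptive: with perhaps two to four affected patients under the 5-10% assumption, a comparison of event rates by steroid cover would tell almost nothing.

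The cost is protocol wording, any schedule entry that follows from the clinicians' choice, one CRF item per intrathecal dose and one listing. No new patient procedure is needed.

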## 8.2. Prohibited therapy

The following medications and supportive therapies are prohibited at all times:

- Any antineoplastic agent other than those planned by the study program.
- Any experimental agent

# 9. STUDY EVALUATIONS

## 9.1. Study Procedures

### 9.1.1. Overview

Patients participation will include:

1. The pretreatment (screening) phase will be 30 days for all laboratory tests and radiographic imaging phase and up to 60 days for orchectomy and bone marrow evaluation.
2. The open label treatment phase will extend from the first day of the first course of R-CHOP to a maximum of 6 courses.
3. The consolidation phase will extend from the first day of the first course of Intermediate-dose MTX to the end of radiotherapy.
4. The follow-up phase will begin after the completion of the consolidation phase. Follow-up will continue until disease progression (PD), patient withdrawal, death or the study completion (expected to be 36 months from the date of the last patient's end of therapy).

Hematology results must be available and reviewed by the investigator to evaluate for possible hematological toxicity.

All subjects will be monitored for adverse events throughout the study and for 30 days after the end of treatment.

### **9.1.2. Pretreatment (screening) phase**

All patients must satisfy all the inclusion criteria and none of exclusion criteria listed in section 4.2 and 4.3 and sign informed consent before the first dose of study drug can be administered. Results of procedures performed as part of standard medical care before signing the informed consent may be used as part of the screening evaluation if performed within 30 days of beginning of therapy for laboratory tests and imaging studies, within 60 days for orchietomy and bone marrow biopsy and aspirate.

- Complete medical history
- Concomitant diseases and treatment
- Recent clinical history (B symptoms)
- Physical examination (size of lymph nodes, sign of organ involvement)
- ECOG performance status
- ECG and echocardiogram or blood pool cardioscintigraphy
- Bone marrow biopsy and aspirate
- Orchietomy
- Chest and abdomen computer tomography; CT of the head and neck at the discretion of the treating physician
- Testicular ultrasound
- CT-PET scan (if possible, recommended but not mandatory)
- Hematology (hemoglobin, WBC and differential, Platelets)
- Blood chemistry (AST, ALT, ALP, total bilirubin, creatinine, albumin, serum LDH)
- Clearance creatinine
- Beta-2-microglobulin
- IgA, IgG, IgM
- HIV
- HBsAg, HBsAb, HBcAb and HBV-DNA, HBV-DNA in case of HBcAb+
- HCVAb, HCV-RNA in case of HCVAb+
- Lumbar puncture for determination of cell count, differential, cytologic and flow cytometry examination in patients with neurologic symptoms and/or clinical suspicion of meningeal lymphoma involvement
- Additional assessments if necessary according to the local standards and if clinically indicated at the discretion of the treating physician.
- Written informed consent.

### **9.1.3. Treatment phase**

Before each course the following parameters will be evaluated:

- Physical examination
- Hematology (Whole blood cell counts and differential)
- Blood chemistry (AST, ALT, ALP, LDH, total bilirubin, creatinine, albumin).
- determination of cell count, differential, cytologic and flow cytometry examination of CNS fluid (during the planned 4 IT therapies)

#### **9.1.4. Intermediate evaluations (after third course of R-CHOP)**

- Physical examination (size of lymph nodes, signs of organ involvement)
- ECOG performance status
- Hematology (hemoglobin, WBC and differential, Platelets)
- Blood chemistry (AST, ALT, ALP, total bilirubin, creatinine, albumin, serum LDH)
- Chest and abdomen computer tomography; CT of the head and neck at the discretion of the treating physician
- Testicular ultrasound
- Additional assessments if necessary according to the local standards and if clinically indicated at the discretion of the treating physician.
- Interim CT-PET scan is advisable, if previously positive, according to local policy but it is not mandatory.

All patients with disease in CR, PR will continue the trial.

All patients in SD/PD will be withdrawn from the study and evaluated as treatment failure

#### **9.1.5. Consolidation phase**

Before each course the following parameters will be evaluated:

- Physical examination
- Hematology (Whole blood cell counts and differential)
- Blood chemistry (AST, ALT, ALP, LDH, total bilirubin, creatinine, albumin)
- Clearance creatinine

